6.2.2 Exclusion Criteria

A patient will be excluded from the study if any of the following criteria are met:

- 1. Patients not currently on dialysis who are likely to initiate routine dialysis during study participation;
- 2. For severe CKD patients on hemodialysis, noncompliance with hemodialysis treatment that, in the opinion of the Investigator, would impede completion or validity of the study;
- 3. Scheduled to receive a kidney transplant during the study;

4. Has a concomitant disease or any medical condition that, in the opinion of the Investigator, could pose undue risk to the patient, impede completion of the study procedures, or would compromise the validity of the study measurements, including, but not limited to:
 - a. Known or suspected history of alcohol, narcotic, or other drug abuse, or substance dependence within 12 months prior to screening;
 - b. Significant systolic or diastolic heart failure (eg, New York Heart Association Class IV congestive heart failure [[Appendix 1, Section 14.1](#)]);
 - c. Severe mental illness or cognitive impairment (eg, dementia);
 - d. Any other relevant acute or chronic medical or neuropsychiatric condition;
5. New or change of treatment received for itch including antihistamines and corticosteroids (oral, IV, or topical) within 14 days prior to screening;
6. New or change of prescription for opioids, gabapentin, or pregabalin within 14 days prior to screening;
7. Serum alanine aminotransferase or aspartate aminotransferase greater than 2.5 times the reference upper limit of normal (ULN), or total bilirubin greater than 2 times the ULN at screening;
8. Received another investigational drug within 30 days prior to the start of screening or is planning to participate in another clinical study while enrolled in this study;
9. Has pruritus attributed to a cause other than CKD (eg, patients with concomitant pruritic dermatological disease or cholestatic liver disease would be excluded);
10. Has localized itch restricted to the palms of the hands;
11. Anticipates receiving an opioid antagonist (eg, naloxone, naltrexone) or opioid-mixed agonist-antagonist (eg, buprenorphine, nalbuphine) from the start of screening through the end of the Treatment Period;
12. Received ultraviolet B treatment within 30 days prior to the start of screening or anticipates receiving such treatment during the study;
13. Participated in a previous clinical study with CR845.
14. If currently a patient with a renal transplant:

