8 STATISTICAL METHODS

8.1 General statistical conventions

All statistical procedures will be completed using SAS version 9.2 or higher.

Unless otherwise noted, continuous variables will be summarized using descriptive statistics, including number of patients with non-missing observation (n), mean, median, standard deviation (SD), minimum (min) and maximum (max). Means and medians will be reported to one decimal place more than the raw data. Standard deviation will be reported to two more decimal places than the raw value. The minimum and maximum will be reported to the same decimal as the raw data.

Categorical variables will be summarized using the frequency count and the percentage of patients in each category. All percentages will be rounded to one decimal point. The number and percentage of patients will always be presented in the form XX (XX.X%) where the percentage is in parentheses. To ensure completeness, all summaries for categorical and discrete variables will include all categories, even if none of the patients in a particular category. Counts of zero in any category will be presented as “0”. Unless otherwise noted, for all percentages, the number of patients in the analysis population for the treatment group will be the denominator.

“Baseline” will be defined as per [section 7.1](#). For efficacy endpoints, “on-treatment” is defined as any assessment following the first dose of study drug and within 2 days from the last dose of study drug recorded in the patient diary. For safety endpoints (excluding adverse events), any assessment within 7 days after last dose of study drug will be deemed “on-treatment”. For all endpoints “End of treatment” (EOT), in summaries, will be represented by the last non-missing on-treatment value recorded up to and including the Week 12/Early Termination visit. Treatment emergence for adverse events is described in [section 8.7.1](#). Summaries will be presented across all scheduled visits and EOT unless stated otherwise. Only on-treatment data will be used in summaries and statistical analyses (with the exception of the Patient Global Impression of Change).

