8.7.2 Clinical laboratory evaluations

Blood samples for clinical laboratory tests, including hematology, serum chemistry and serum pregnancy will be collected during screening and day 1 before study drug administration, on week 6 and week 12 (end of treatment).

All clinical laboratory data will be reported in Système International units.

Summary statistics for each scheduled time point measured and mean changes from baseline to each time point will be presented for hematology and serum chemistry laboratory results. The baseline value is defined as the last observation prior to or on the date of the first dose of study drug whether scheduled or unscheduled (see [section 7.1](#)).

Hematology and serum chemistry laboratory test results will be assigned as Low (L), Normal (N) or High (H) classification according to whether the value was below (L), within (N), or above (H) the laboratory parameter’s reference range.

Statistical Analysis Plan (SAP)

Comparisons will be based on 3×3 tables (shift tables) that, for a particular laboratory test, compare the baseline L/N/H classification to the highest and/or lowest L/N/H classification during the treatment period.

Clinically important laboratory values based on the below specified criteria will also be summarized.

- Alanine aminotransferase (ALT), aspartate aminotransferase (AST),
 - $>3 \times$ ULN
 - $>5 \times$ ULN
 - ALT $>3\times$ ULN or AST $>3\times$ ULN
- Alkaline phosphatase (ALP)
 - $>1.5 \times$ ULN
- Total Bilirubin (TBILI)
 - $>2 \times$ ULN
- AST and Total Bilirubin
 - AST $>3\times$ ULN and TBILI $>2\times$ ULN
- ALT and Total Bilirubin
 - ALT $>3\times$ ULN and TBILI $>2\times$ ULN
- AST or ALT and Total Bilirubin
 - AST or ALT $>3\times$ ULN and TBILI $>2\times$ ULN

A summary of treatment emergent sodium findings will also be provided, categorizing results into those <146 mmol/L, $146 - 150$ mmol/L, and >150 mmol/L at the 6 and 12 week assessments. An additional summary will present these categories for subjects over the full study period presenting the highest category attained (at any on-treatment assessment) and sustained (at any on-treatment assessment and all subsequent on-treatment assessments); this analysis will include both scheduled and unscheduled laboratory test results.

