All clinical laboratory values will be presented in a listing. Additionally, ALT, AST, bilirubin, ALP and sodium will be presented in a separate listing, with values $>3 \times$ or $>5 \times$ ULN flagged for alanine aminotransferase and aspartate aminotransferase; $2 \times$ ULN flagged for total bilirubin, $1.5 \times$ ULN flagged for alkaline phosphatase and ≥ 146 mmol/L flagged for sodium. In each listing, all the data for the patient across the study will be presented for any parameter flagged post-baseline.

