8.7.3 Vital signs

Vital sign parameters include systolic blood pressure (SBP), diastolic blood pressure (DBP), body temperature and heart rate. For each scheduled timepoint, descriptive summary statistics will be calculated for both the actual and the change from baseline values for all

Statistical Analysis Plan (SAP)

vital sign parameters. The baseline value is defined as the last observation prior to or on the date of the first dose of study drug whether scheduled or unscheduled (see [section 7.1](#)).

Clinically notable vital signs will be identified based on the criteria below. For each vital sign parameter, the number and percentage of subjects with at least 1 notable value will be tabulated by week and overall for Treatment period. This analysis will include results from both scheduled and unscheduled assessments.

Vital Sign Parameter	Value
Systolic blood pressure	≥ 180 mm Hg
	≤ 90 mm Hg
Diastolic blood pressure	≥ 100 mm Hg
	≤ 60 mm Hg
Heart rate	>130 bpm
	<55 bpm

All vital signs will be listed in patient listings, including visit and collection date/time, and will be sorted by patient identifier and date/time of assessment.

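### The sodium summary in SAP 8.7.2 is labelled treatment emergent but never refers to baseline, so values already high before dosing are counted as emergent (minor)

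*SAP*

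**What the plan says.** SAP 8.7.2 introduces the display with "A summary of treatment emergent sodium findings will also be provided, categorizing results into those" below 146, 146 to 150 and above 150 mmol/L at the Week 6 and Week 12 assessments. A second summary covers the whole study and gives the "highest category attained (at any on-treatment assessment) and sustained (at any on-treatment assessment and all subsequent on-treatment assessments"), using scheduled and unscheduled results.

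Two definitions in SAP 8.1 govern how this is read. For safety data other than adverse events, on-treatment is a matter of timing: "any assessment within 7 days after last dose of study drug will be deemed" on-treatment. Emergence is defined for adverse events alone: "Treatment emergence for adverse events is described in" section 8.7.1. No definition of emergence is given for a laboratory value.

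The interim safety package in SAP 8.9.2.5 includes a summary of abnormal sodium findings at the same 146 and 150 cut-offs, again with no baseline condition.

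Two neighbouring displays also use absolute cut-offs, under different labels. Alkaline phosphatase (ALP) above 1.5 x ULN comes under "Clinically important laboratory values based on the below specified criteria will also be summarized". For vital signs, "the number and percentage of subjects with at least 1 notable value will be tabulated by week and overall for Treatment period" (SAP 8.7.3).

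**The concern.** A table called treatment emergent is normally read as showing what appeared or worsened after dosing. This one shows where patients were while on treatment. Its lowest category, below 146 mmol/L, cannot be an emergent abnormality at all, which suggests that the label was attached without a rule behind it. The sustained column is the most exposed part, because a stable pre-existing elevation is the kind of value most likely to persist at every later assessment.

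Sodium matters here because protocol 4.3 lists hypernatremia among the consequences of the drug's fluid effects, and this is the planned readout of sodium by clinical cut-off. Entry criteria limit some laboratory values (protocol 6.2.2, in the exclusion that begins "Serum alanine aminotransferase or aspartate aminotransferase greater than 2.5 times the reference upper limit of normal (ULN), or total bilirubin greater than 2 times"), but none limits sodium. Patients may therefore enter at 146 mmol/L or above, and the summary cannot separate them from patients who reached that level on study drug.

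**Working it through.** The plan states no figure for this point, so there is none to reproduce. The check is first textual, then a sizing under stated assumptions.

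**1. Three hypothetical patients under the written rule**

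| Day 1 (pre-dose) | Week 6 | Week 12 | Highest attained | Sustained | Worse category than baseline? |
|---|---|---|---|---|---|
| 148 | 148 | 148 | 146-150 | 146-150 | No |
| 142 | 148 | 148 | 146-150 | 146-150 | Yes |
| 148 | 152 | 152 | >150 | >150 | Yes |

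The first two patients fall in identical cells, although only the second changed. The last column is what the label implies and what the rule does not compute.

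**2. Can another planned summary by arm recover it?**

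- The L/N/H shift tables in 8.7.2 compare baseline with the highest or lowest on-treatment class, but they cut at the laboratory reference range. The documents do not give that range for sodium. If its upper limit is 145 mmol/L (assumption), the normal-to-high shift equals the shift from below 146 to 146 or above. Even then, 146-150 and above 150 both fall in the high class and cannot be told apart.
- Mean change from baseline, and the interim line plots of change over time, use baseline but not the cut-offs.
- The flagged-value listing shows all of a flagged patient's data, so baseline can be read there, one patient at a time and not as a count by arm.

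**3. Size of the miscount**

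Inputs: n = 60 per arm (SAP 5). Share starting at 146 mmol/L or above, p0 = 2% to 10% (assumption). All of these patients stay there (assumption).

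- Patients counted per arm with no drug effect = n x p0: 60 x 0.02 = 1.2; 60 x 0.10 = 6.
- SD of the between-arm difference in these counts = sqrt(2 x n x p0 x (1 - p0)): sqrt(2 x 60 x 0.02 x 0.98) = 1.5; sqrt(2 x 60 x 0.10 x 0.90) = 3.3 patients.
- Interim: 50% to 60% of 240 is 120 to 144 patients, or 30 to 36 per arm. The count runs from 30 x 0.02 = 0.6 to 36 x 0.10 = 3.6 per arm.

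**4. Dilution of a real effect**

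For illustration, assume new-onset rates r of 5% on placebo and 15% on one dose, a true risk ratio of 3.0 and a true difference of 10 points. With persistence s, the expected share counted is p0 x max(s, r) + (1 - p0) x r.

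- p0 = 10%, s = 100%: placebo 0.10 + 0.90 x 0.05 = 0.145 (8.7 of 60); active 0.10 + 0.90 x 0.15 = 0.235 (14.1 of 60). Ratio 1.62, difference 9 points.
- p0 = 10%, s = 50%: placebo 0.05 + 0.045 = 0.095; active 0.05 + 0.135 = 0.185. Ratio 1.95.
- p0 = 2%, s = 100%: placebo 0.02 + 0.98 x 0.05 = 0.069; active 0.02 + 0.98 x 0.15 = 0.167. Ratio 2.42.
- p0 = 0: ratio 3.0; the table is unaffected.

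The ratio shrinks much more than the difference. Among patients with baseline below 146, a cross-tabulation returns 5% against 15%, ratio 3.0, whatever p0 is.

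**The case against.** The strongest reply is that this is a labelling slip in a descriptive table, surrounded by displays that do use baseline. Protocol 8.7 plans no inferential safety statistics. A randomized placebo arm is shown alongside. Under protocol 6.5.2.1.1 a laboratory abnormality becomes an adverse event only if it is new and clinically significant or symptomatic, or a clinically significant worsening, so important sodium changes also reach the TEAE tables with a baseline comparison built in. Protocol 4.3 describes the fluid effects in people with normal renal function; it says that they appear absent in dialysis patients and expects them to be largely reduced in stage III to IV disease. The table shells are in a separate document and may already print a baseline column. All of this stands, and it is why the point is minor. It does not supply the missing definition, nor a count by arm at 146/150 that takes baseline into account.

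A reader might infer three stronger things that the documents do not support.

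- *That the ALP and vital-sign tables have the same fault.* They are labelled clinically important and notable, not emergent, and a value beyond the cut-off after dosing is an on-treatment finding under 8.1. The entry "flagged for alkaline phosphatase" is a listing flag and counts nobody; the count is in the summary. Both tables lack a baseline reference at their cut-offs, but that is a choice of display.
- *That the summary is biased for or against a dose.* Pre-existing values are expected equally in all randomized arms. The result is dilution plus chance imbalance.
- *That it would mislead the interim decision on dropping doses.* SAP 8.9 ties no dose decision to a sodium count, and the interim package also contains change-from-baseline plots for sodium and listings of clinically important laboratory values.

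**Conclusion.** The point holds for sodium. The label in SAP 8.7.2 promises a comparison with baseline that the rule does not make, and no other planned summary by arm makes it at both cut-offs. The interim summary has the same gap, though its own title does not use the word emergent.

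Severity is minor. The size cannot be taken from the documents: the figure of about 1 to 6 of 60 patients per arm rests on an assumed 2% to 10% baseline prevalence and full persistence, and falls to nothing if no one starts at 146 mmol/L or above. The dilution figures also rest on assumed new-onset rates. If the sodium reference limit is 145 mmol/L, the shift tables already recover the lower cut-off and the remaining gap is the split at 150.

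**What to change.** In SAP 8.7.2, present the sodium summaries as baseline category (below 146, 146-150, above 150 mmol/L) by highest attained on-treatment category, and likewise by sustained category, for each arm. Reserve the term treatment emergent for an on-treatment category worse than the baseline category. Use the same layout for the interim summary in 8.9.2.5.

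Keep all patients in the table. Restricting it to those below the cut-off at baseline would hide further worsening, such as the move from 148 to 152 mmol/L in the third example.

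Optionally, add the same cross-tabulation to the ALP summary and the notable vital-sign table.

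The cost is slightly larger tables and minor programming. Day 1 pre-dose chemistry is already scheduled and baseline is already defined in SAP 7.1, so no new data are needed. If the separate shells already show baseline at these cut-offs, only the wording in 8.7.2 and 8.9.2.5 has to change.

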8.7.3 Vital signs

Vital sign parameters include systolic blood pressure (SBP), diastolic blood pressure (DBP), body temperature and heart rate. For each scheduled timepoint, descriptive summary statistics will be calculated for both the actual and the change from baseline values for all

Statistical Analysis Plan (SAP)

vital sign parameters. The baseline value is defined as the last observation prior to or on the date of the first dose of study drug whether scheduled or unscheduled (see [section 7.1](#)).

Clinically notable vital signs will be identified based on the criteria below. For each vital sign parameter, the number and percentage of subjects with at least 1 notable value will be tabulated by week and overall for Treatment period. This analysis will include results from both scheduled and unscheduled assessments.

Vital Sign Parameter	Value
Systolic blood pressure	≥ 180 mm Hg
	≤ 90 mm Hg
Diastolic blood pressure	≥ 100 mm Hg
	≤ 60 mm Hg
Heart rate	>130 bpm
	<55 bpm

All vital signs will be listed in patient listings, including visit and collection date/time, and will be sorted by patient identifier and date/time of assessment.

8.7.4 Electrocardiograms

ECG assessment will be done at screening, day 1 and end of treatment (EOT).

ECG results include an overall interpretation of 'normal,' 'abnormal but not clinically significant,' or 'abnormal and clinically significant.' These results will be tabulated at each time point using a shift table.

Electrocardiogram results will be listed for all available visits, including visit, whether ECG was performed (yes/no), explanation (if not performed), assessment date/time, overall interpretation.

Statistical Analysis Plan (SAP)

8.8 Other analysis

8.8.1 Subgroup analysis

The following endpoints will be summarized by strata- patient's renal disease status: moderate CKD non-dialysis; severe CKD non-dialysis; and severe CKD on dialysis.

- All primary and secondary efficacy endpoints
 - 24-hour Worst Itching Intensity numerical rating scale (NRS) score
 - Total Skindex-10 Scale score
 - 5-D Itch Scale score
- Safety endpoints
 - Overall Adverse Events
 - AEs by SOC and PT

8.9 Interim analysis

An unblinded Interim Analysis (IA) will be conducted when approximately 50-60% of the planned 240 patients have been randomized and have either completed the 12-week Treatment Period or have discontinued study drug early. The primary goal of the IA is to identify dose(s) of oral CR845 that are both safe and efficacious across all strata. Doses that are found to be unsafe or poorly tolerated will be dropped from the study. No dose will be dropped for futility reasons. The sample size will not be increased past 480 total patients (120 patients per treatment group).

8.9.1 General Strategy

Since there are 3 CR845 doses, the decision rule for sample size re-estimation to be followed for the IA, and described below is designed to address multiple comparisons and protect the type 1 error

The conditional power of each CR845 dose to separate from placebo at the end of study (based on the planned sample size of 60 patients per group) will be calculated, assuming that estimated treatment effect at interim analysis is the true effect.

- If the conditional power is $\geq 80\%$ for at least one dose then the sample size will not be increased in any of the doses
- If the conditional power is $< 80\%$ across all doses and $\geq 20\%$ in at least one dose,

Statistical Analysis Plan (SAP)

then the following process will be followed

- For each CR845 dose group the sample size ($size_{new}$) needed to achieve an 80% power given the observed treatment effect will be calculated
- The calculated sample sizes will be ordered from lowest to highest as $\min(size_{new})$, $\text{int}(size_{new})$ and $\max(size_{new})$
- If the smallest re-estimated sample size $\min(size_{new})$ is > 120 then the recommendation will be to increase the sample size to 120 for all treatment groups
- If $\min(size_{new}) \leq 120$ but $\{\text{int}(size_{new}) \text{ and } \max(size_{new})\} > 120$ (i.e. only the minimum sample size is ≤ 120) then the recommendation will be to increase the sample size to $\min(size_{new})$ for all treatment groups
- If $\min(size_{new})$ and $\text{int}(size_{new})$ are both ≤ 120 (i.e. 2 out 3 re-estimated sample sizes are ≤ 120) then the recommendation will be to increase the sample size for all treatment groups to
 - $\text{int}(size_{new})$ if $[\text{int}(size_{new}) - \min(size_{new})] \leq 10$

or

- $\min(size_{new})$ if $[\text{int}(size_{new}) - \min(size_{new})] > 10$
- If $\max(size_{new}) \leq 120$ (i.e. 3 out 3 re-estimated sample sizes are ≤ 120), then the recommendation will be to increase the sample size for all treatment groups to
 - $\max(size_{new})$ if $[\max(size_{new}) - \min(size_{new})] \leq 10$

or

- $\min(size_{new})$ if $[\max(size_{new}) - \min(size_{new})] > 10$
- If the conditional power is $< 20\%$ for all doses the sample size will not be increased for any dose

Conditional power will be calculated for each CR845 dose assuming that the estimated treatment effect at interim analysis is the true effect as proposed by formula in the article by Mehta and Pocock³.

$$CP_{\hat{\delta}_1}(z_1, \tilde{n}_2) = 1 - \Phi \left(\frac{z_2\sqrt{n_2} - z_1\sqrt{n_1} - \frac{z_1\sqrt{\tilde{n}_2}}{\sqrt{n_1}}}{\sqrt{\tilde{n}_2}} \right).$$

Where Z_1 is observed test-statistic calculated using the sample included in the IA, n_2 is the total planned size (i.e. $120 = 60$ per group), n_1 is the interim size (approximately 50% of the target n_2), \tilde{n}_2 is the difference ($n_2 - n_1$), and δ is the observed treatment difference.

Statistical Analysis Plan (SAP)

8.9.2 Interim Analysis Statistical Analysis

The following variables/summaries will be included in the Interim Analysis

8.9.2.1 Subject disposition including study population

Subject disposition information will be summarized by treatment group and overall (across CR845 doses and across all treatments). The number of patients who are enrolled, the number and percent of screen failures, of randomized and treated patients will be summarized. In addition, the reason for screen failure will be provided. In this summary table, percentages will be calculated using the number of enrolled patients as the denominator.

A separate display will present the number and percent of patients who complete the 12-week study treatment, who discontinue from double-blind treatment, (and the reason for study treatment discontinuation), and who complete the follow-up. For this table, percentages will be calculated using the number in patients in the safety population.

Additionally, the above table will summarize the number and percent of randomized patients in the following populations:

- Full Analysis set;
- Safety population;

